1. BACKGROUND AND SIGNIFICANCE

Perimenopausal Depression: Midlife women are burdened with depression risk that is at least partly attributed to changing reproductive steroid dynamics across a prolonged reproductive transition. Perimenopause (Peri) confers a specific period of risk in women for subthreshold depressive symptoms and major depressive episodes (MDEs).¹ Indeed, women are twice as likely to experience MDEs in Peri than in late premenopause.^{2,3} MDEs during Peri represent depression recurrence for most affected women, but 45%–68% of women without a history of major depressive disorder (MDD) develop at least subsyndromal depressive symptoms during Peri.¹ While less severe than MDE, subsyndromal depression also causes significant distress and impairs quality of life.^{4,5} Perimenopausal depression (PeriDep) encompassing MDEs and subthreshold depression is common in women.

PeriDep shares risk factors with depression occurring at other life stages,¹ but also has unique risk factors including hot flashes [or vasomotor symptoms (VMS)], depression during other reproductive transitions, and sleep disturbance. Sleep disturbance is both a symptom of and causal for depression.^{6–8} Sleep problems are prevalent among Peri women due to nocturnal VMS, which lead to increased time spent awake after sleep-onset (WASO), the most prominent Peri sleep problem.⁹ However, sleep-onset problems and shorter total sleep time can also occur.¹⁰ Selective association of PeriDep with nocturnal VMS⁹ suggests that mechanistic processes underlying VMS at night¹¹ are especially disruptive to mood in Peri women.

PeriDep, postpartum depression (PPD), and premenstrual dysphoric disorder (PMDD) are reproductive–endocrine (reprotoendo) mood disorders unique to women.¹² Each represents a vulnerable period for depression that is both temporally and causally linked to changing reproductive steroids. In all three disorders, estradiol (E2) and progesterone (P4) levels decline.^{13–15} Because the P4 mechanism has been targeted effectively in PPD through its allopregnanolone (ALLO) metabolite,¹⁶ the P4 withdrawal shared between disorders suggests that similar strategies may be effective therapy for PeriDep. Shared risk factors and parallel underlying reproductive steroid changes substantiate significant overlap between the reproductive-endocrine mood disorders of PeriDep, PPD, and PMDD. While synthetic P4 preparations anecdotally worsen mood in PeriDep, empiric studies find no adverse mood effects.¹⁷ Our findings that ovulatory levels of P4 correlate with better mood¹³ support the observation that natural P4 administration improves mood in PeriDep,^{18,19} and our premise that ALLO administration improves PeriDep through the proposed behavioral and neurobehavioral mechanisms.

Changes in Endogenous Allopregnanolone (enALLO) as a Mechanism Underlying PeriDep: How P4 and its metabolites alter mood in PeriDep is unclear.²⁰ One plausible mechanism is through P4 metabolism to the endogenous neurosteroid ALLO.^{21,22} Levels of enALLO mirror those of P4—increasing across pregnancy, in the menstrual cycle luteal phase, and when P4 is added to postmenopausal hormone therapy,²³ and decreasing postpartum and across menopause.^{24,25} Through gabaaminobutyric (GABA)_A receptor activity, enALLO can rapidly impact mood, but other critical biological mechanisms discussed below may also translate these benefits. Changes in enALLO influence mood via regulation of neuronal function involved in both emotion and sleep/wakefulness. Ovulation triggers high systemic levels of P4, a precursor that stimulates

enALLO production; conversely, when P4 declines, reduced enALLO production may promote emergence of depression in repro-endo mood disorders, as suggested in studies of women who have PPD or PMDD, or across the menopause.^{25,26} Symptoms of PMDD are averted by blocking P4 conversion to enALLO premenstrually,²⁷ and PPD symptoms are triggered when GABA receptor responsivity²⁸ to peripartum enALLO²⁹ activity is suppressed. enALLO levels are also lower in depressed than non-depressed women during premenopause, late Peri, and also postmenopause.^{24,30-32} We hypothesize that falling enALLO levels across menopause underlies PeriDep. Taken together, evidence of analogous changes in endogenous progesterone and ALLO, alongside ALLO dysregulation during PPD, PMDD, and PeriDep, and data supporting the efficacy of exogenous ALLO for PPD, suggest that exogenous ALLO will exert its effects through similar behavioral and neural mechanisms in women with PeriDep.

Exogenous ALLO (exALLO) as a Mechanistic Probe in PeriDep: The gradual process through which P4 declines across Peri and the expected parallel changes in enALLO make exploration of ALLO's mechanistic effects on behavioral and neurobiological processes underlying depression challenging to quantify. Thus, we propose a mechanistic trial to amplify contrast between lower enALLO levels in Peri and higher levels experimentally induced by exALLO. We will follow the exALLO treatment studied in PPD patients using FDA-approved brexanolone,¹⁶ which has proven antidepressant efficacy.³³ Brexanolone will be used as it is FDA-approved for the same indication of depression in a different population of women that has shared underlying neural mechanisms and for which substantial safety data are available. This specific source of exogenous ALLO was selected as the probe in this study because it is the pure form of ALLO mimicking the endogenous ALLO neurosteroid, which is the mechanism under investigation. Brexanolone optimizes the ability to test the mechanistic hypotheses in a controlled laboratory setting using a rigorous experimental design. By manipulating ALLO levels together with measurement of key depression-driving constructs, this powerful approach harnesses the endocrine biology of Peri to rigorously explicate behavioral and neurobiological mechanisms underlying depression in Peri women.

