Informed Consent and Assent: Participants will not undergo any study procedures until they understand the risks and benefits and provide written and informed consent to participate. At part 1 of 2 of the screening visit, the consenting study physician will review the consent form in its entirety with prospective participants utilizing REDCap. The consent form will include information about the risks and benefits of study participation and contact information for the study investigators and research staff. The consent will include information about all study risks, including those related to the infusion of brexanolone or saline. Participants enrolling in the study must understand the nature of the study, the discomforts/risks, and potential benefits. Any questions or areas of concern regarding the protocol will be addressed. The participants may choose to have a confidant with them during the consent procedure. If potential participants feel comfortable with the study procedures, they and the study physician will sign the consent form. Enrolled participants will be given a copy of the completed consent form before any study procedures are completed, and a copy of the signed consent form and documentation of the informed consent process will be stored in the participant's research file.

If participants have reservations about study participation at the first visit, they will have the option to take the consent form home to consider the decision to participate in the study and to consult with their family and health-care providers. They can return at a later date to discuss the study again before signing the consent form and initiating study procedures.

The study protocol, informed consent form, telephone and REDCap screens, and all other study procedures will be approved by the IRB before the study is initiated.

Double-blind Randomization: Subjects will be randomized 1:1 to brexanolone or saline infusion, stratified by use of psychotropic medication to treat depression status. Treatment allocation will be known only by the biostatistical consultant, Safety Monitoring Group, and BWH Investigational Drug Service, the latter of whom will determine the permuted block randomized assignment. Subjects and study staff will be blinded until primary analyses are done, unless unblinding is required for safety.

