6. STUDY PROCEDURES

This study is a randomized, double-blind, mechanistic placebo-controlled trial that involves a 60-hour infusion of either brexanolone or placebo. All participants will undergo the same procedures, which include: remote (part 1) and in-person (part 2) screening visit, four-night inpatient visit, optional functional brain MRI studies, interim remote visit, and 30-day follow-up in-person visit.

Screening Visit: All interested participants who appear eligible based on a telephone pre-screening will attend a remote visit to initiate the screening visit (part 1 of 2) followed by in-person screening visit (part 2 of 2) at a BWH Center for Clinical Investigation (CCI) outpatient unit.

At the remote visit, a study physician will first obtain written, informed consent from participants, who will then be assessed further for eligibility. Procedures will include:

- a medical evaluation to ensure medical appropriateness for the study
- administration of the Mini International Neuropsychiatric Interview (MINI)
- administration of the HDRS-17
- administration of the C-SSRS
- MRI safety screening
- completing self-administered questionnaires and surveys

At the in-person visit, assessment for eligibility will be finalized. Procedures will include:

- continuation of a medical evaluation to further ensure medical appropriateness for the study
- measurement of vital signs and anthropomorphic features
- having one blood draw for eligibility/safety labs and for reproductive hormones

Eligible participants will be asked to complete a week-long daily diary monitoring their sleep, vasomotor symptoms (VMS) and menstrual bleeding pattern at home.

Optional pre-admission MRI Visit: resting-state functional MRI (rfMRI) / magnetic resonance spectroscopy (MRS) scans (before the infusion).

-1 Day to Inpatient Visit*: The HDRS-17 will be administered remotely prior to inpatient stay to confirm state of depressive symptoms. *If the pre-admission MRI is completed within a reasonable time frame to confirm state of depressive symptoms prior to inpatient stay the HDRS-17 can be done at this visit in lieu of -1 Day remote assessment.

Four-Night Inpatient Visit: Participants will be admitted to BWH CCI Intensive Physiologic Monitoring Unit (IPM) for four consecutive nights, which will include the following procedures:

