- The 60-hour brexanolone vs placebo infusion will begin in the evening of the 2nd inpatient night and end on the last morning immediately preceding post-treatment assessments
- Safety assessments will be conducted daily throughout the infusion and inpatient stay
- 2 electroencephalography (EEG) recordings (one before infusion and one during the final night of the infusion)
- At least once daily assessments of rumination, attentional bias, psychomotor vigilance, mood state (POMS), and depressive symptoms (before and after the infusion)
- Daily blood draws (before and after the infusion). Blood will be collected to run assays, including brain derived neurotrophic factor (BDNF), inflammatory biomarkers, reproductive hormones, serum ALLO levels, and serum for future analyses.
- One urine collection at admission for HCG, one at morning void after first night for melatonin. If there happens to be overnight voiding on first night additional samples will be requested but there is no scheduled collection, it will only be done if the participant is awake to void on their own.

Optional post-admission MRI Visit: resting-state functional MRI (rfMRI) / magnetic resonance spectroscopy (MRS) scans (after the infusion)

Interim Follow-Up and Remote Visit: During the 1-month follow-up period after participants are discharged from the inpatient visit, participants will be asked to complete daily monitoring of their sleep, VMS, and menstrual cycle patterns.

One remote interim visit approximately 2 weeks after the inpatient visit will take place to monitor adverse events, administer the C-SSRS, and assess mood state (POMS) and depressive symptoms.

Follow-Up In-Person Visit: Approximately 30 days after treatment initiation, participants will have a final follow-up in-person visit, during which they will undergo:

- Adverse event and safety monitoring
- Optional rfMRI/MRS scanning procedures
- Behavioral assessments including depressive symptom severity, mood state (POMS), rumination, and attentional bias, psychomotor vigilance; and
- Blood draw for neuroprotective and inflammatory biomarkers, reproductive hormones, ALLO levels, and serum for future analyses.

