Analysis Plan: Briefly, primary analyses will compare exALLO and placebo subject-level response profiles from baseline to 4-day in each primary outcome to examine acute effects. Secondary analyses will compare exALLO and placebo subject-level response profiles from baseline to 30-day in those same outcomes to examine durability of effects. Analyses of secondary outcomes will be conducted in parallel with those for primary outcomes. Key covariates (e.g., age, race, body mass index, socioeconomic status and stressful events) will be measured and considered a priori as potential predictors in multivariate analyses to reduce unexplained variability. Analytic outcomes can be transformed as needed to satisfy model assumptions such as normally distributed residuals for linear models or, alternatively, non-linear distribution models (e.g., negative binomial, lognormal, or gamma) can be applied in the generalized linear mixed model approach to model the observed distribution of the outcome. Model selection will be based on Akaike information criterion or quasi-likelihood under the independence model criterion values. We will use the False Discovery Rate (FDR) correction⁴⁵, which allows for robust retention of alpha to remain at 5% for each statistical test with the additional constraint of q-threshold also set to 5% (i.e., acceptable FDR of 5%). This analytic approach is advantageous over Bonferroni adjustment and other approaches that adjust the 5% alpha threshold as it will not increase the chance of inflating Type II error given the number of primary outcomes in Aims 1 and 2.

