The proposed sample size (n=80; 40 per arm) will yield more than 80% power to detect effect sizes 0.64 or larger in a two-tailed, two-sample contrast of group-level means, consistent with our primary analysis plan to assess acute treatment effect (4-day) of exogenous ALLO compared to placebo. Furthermore, this approach avoids a priori presumptions to be made on data distribution and impact of potential covariates (i.e., linear vs. non-linear relationship with the outcome). We conservatively based our anticipated estimates on published effect sizes for progesterone-associated or ALLO-induced changes in behavioral, circuit-based, molecular, and physiological measurements of the RDoC Negative Valence System and Arousal and Regulatory System domains, and when none were available, on our own pilot data. While the sample size justification uses a cross-sectional approach as if there is one measurement per participant, the data and analyses will be longitudinal – accounting for repeated measured per participant, which also will increase power and precision. Therefore, we expect that this mixed-model analytic approach will yield even greater statistical power than the conservative estimates from the simpler approach used for sample size determination.

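### The WASO analysis makes inefficient use of the single night-1 EEG baseline and names neither the pre-admission hot-flash diary nor the sleep diary as a covariate; the cost is precision, not bias

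*Combined protocol and SAP*

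**What the plan says.** Background and Significance (section 1) gives the mechanism: "Sleep problems are prevalent among Peri women due to nocturnal VMS, which lead to increased time spent awake after sleep-onset (WASO". EEG-derived WASO is the outcome of hypothesis 2c (section 2), and the sample-size text in section 9 includes it among the primary contrasts, with an assumed effect above d = 1.

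Study Procedures (section 6) asks eligible women to "complete a week-long daily diary monitoring their sleep, vasomotor symptoms (VMS) and menstrual bleeding pattern at home" before admission. The same section plans "2 electroencephalography (EEG) recordings (one before infusion and one during the final night of the infusion". The infusion starts on the evening of the second inpatient night, so the only pre-infusion EEG is the first night in the unit. No EEG is planned at day 30.

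Section 9 compares subject-level response profiles from baseline to day 4 in a mixed model. The fixed effects are treatment and time, with a subject random intercept. On covariates it says: "Key covariates (e.g., age, race, body mass index, socioeconomic status and stressful events) will be measured and considered a priori". That list consists of examples and does not mention VMS or diary sleep. VMS is not a stratification factor either: "Subjects will be randomized 1:1 to brexanolone or saline infusion, stratified by use of psychotropic medication to treat depression status".

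**The concern.** The protocol identifies a cause of between-woman variation in a primary outcome and measures it before treatment, but does not say the analysis will use it. The EEG baseline is one night in an unfamiliar unit. Section 7 accepts that the recording equipment may reduce sleep quality. A single such night is likely to be a noisy measure of a woman's usual WASO, and the efficiency of a baseline-to-day-4 contrast depends heavily on how well that night correlates with the final one.

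What is at stake is the precision of the test of hypothesis 2c and of WASO as a candidate mediator in Aim 3. Covariates are only considered, and model selection is by information criteria. Whether VMS enters the WASO model could therefore be decided after the data are seen.

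**Working it through.** **Inputs from the documents.** The sample-size text in section 9 plans 80 women, split equally into two groups of 40. Its claim is that this "will yield more than 80% power to detect effect sizes 0.64 or larger in a two-tailed, two-sample contrast of group-level means". Alpha comes from "robust retention of alpha to remain at 5% for each statistical test". Each woman has two EEG nights.

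**Assumed inputs (not in the documents).** ρ is the correlation between night-1 and final-night WASO. c₁ and c₂ are the correlations of pre-admission diary VMS with night-1 and final-night WASO. The SD is the same on both nights and set to 1, with d on that raw SD.

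**1. The plan's own figure.** Noncentral t, 40 per arm, d = 0.64, 78 df: power 80.7%. The stated figure of more than 80% reproduces.

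**2. What the planned contrast does with the baseline.** I read the comparison of response profiles as a treatment-by-time contrast. With two nights, complete data and a random intercept, it equals the difference in mean change, with per-woman variance 2(1 − ρ). With night-1 WASO as a covariate, the variance is 1 − ρ².

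| ρ | change: 2(1 − ρ) | power at 0.64 | covariate: 1 − ρ² | power at 0.64 |
|---|---|---|---|---|
| 0.3 | 1.40 | 66.6% | 0.91 | 84.2% |
| 0.4 | 1.20 | 73.3% | 0.84 | 86.9% |
| 0.5 | 1.00 | 80.7% | 0.75 | 90.4% |
| 0.7 | 0.60 | 95.4% | 0.51 | 97.7% |

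Power uses d = 0.64/√variance, with 78 df (change) or 77 df (covariate). Below ρ = 0.5 the change contrast is weaker than the cross-sectional comparison used for the sample size. The covariate form is better at every ρ shown.

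**3. VMS as a plain main effect in the planned model.** It gains nothing. In one simulated data set (ρ = 0.5, c = 0.4), the standard error of the treatment-by-time term was 0.2177 with and without VMS. When the arms shared a common baseline mean, it fell from 0.195 to 0.183 with VMS.

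**4. VMS added to the baseline-adjusted model.** The share of remaining variance explained is (c₂ − ρc₁)² / [(1 − ρ²)(1 − c₁²)]. At ρ = 0.4:

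| c₁ | c₂ | further cut | residual variance | power at 0.64 (76 df) |
|---|---|---|---|---|
| 0.2 | 0.2 | 1.8% | 0.825 | 87.5% |
| 0.3 | 0.3 | 4.2% | 0.804 | 88.3% |
| 0.4 | 0.4 | 8.2% | 0.771 | 89.6% |
| 0.4 | 0.2 | 0.2% | 0.838 | 87.0% |

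Example, third row: (0.4 − 0.16)² / (0.84 × 0.84) = 0.0576/0.7056 = 8.2%.

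**5. Standard errors at ρ = c = 0.4.** √(variance × 2/40) gives 0.245 (change), 0.205 (night-1 covariate) and 0.196 (plus VMS). Simulation gave 0.240, 0.203 and 0.195.

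**6. At the plan's assumed WASO effect.** At d = 1, the two-sample contrast has 99.3% power. The change contrast at ρ = 0.4 has 98.1%.

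**The case against.** The strongest reply is that the planned contrast already deals with stable hot-flash burden. Such differences act on both EEG nights and largely cancel. This stands. A reader might infer that a chance VMS imbalance between the arms feeds directly into the treatment effect, but the planned analysis does not support that. In simulation with a forced imbalance of 0.4 SD, correlations of 0.4 and no treatment effect, the mean spurious effect on the baseline-to-day-4 contrast was −0.004 SD. It reached 0.16 SD only when day 4 was compared alone, which is not the plan.

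A reader might also infer that WASO will be left unadjusted. The documents do not say so: the covariate list is open, and VMS is unnamed but not excluded.

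Three further points stand. The first-night setting is common to both arms, so it adds noise without bias, and adjusting for VMS does not remove it. The documents do not say that the diary separates night-time from daytime VMS, although the stated mechanism is nocturnal. A VMS gain much above 8% would need the diary to track the final night, under infusion, better than the untreated first night, which is nearer in time. At ρ = 0.4, c₁ = 0.2 and c₂ = 0.5 give 21.9%, but nothing in the documents supports that ordering.

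None of this answers the inefficient use of the night-1 EEG, or the lack of a pre-specified covariate set for this outcome.

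**Conclusion.** The point holds as a low-cost gain in precision, not as a threat to validity. Most of the gain comes from using night-1 WASO as a covariate: at ρ = 0.4, variance falls from 1.20 to 0.84 and power at d = 0.64 rises from 73% to 87%. Diary VMS then adds about 1 to 3 points if it correlates 0.2 to 0.4 with both nights. It adds almost nothing if it tracks night 1 better than the final night. The extra gain from diary wake time was not quantified.

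Every figure beyond the plan's own 80.7% rests on assumed correlations. If the effect is as large as the plan expects, power is about 98% to 99% without any change. The adjustment matters if the effect is nearer 0.64 or below. The plan's estimate comes from exogenous progesterone in postmenopausal women, not from ALLO in this population.

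**What to change.** Before unblinding, state in the SAP that the primary WASO analysis regresses final-night EEG WASO on treatment and night-1 EEG WASO, or uses a mixed model constrained to a common baseline mean. Add these fixed covariates, kept whatever their p-values:

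- the randomisation stratum (psychotropic medication use);
- mean pre-admission diary VMS (nocturnal if recorded, otherwise total);
- mean diary-reported wake after sleep onset over the same week, if the diary records it.

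Say how incomplete diary weeks are averaged. Use no VMS recorded during the infusion: section 7 lists flushing and hot flush as drug effects, so that measure could itself be changed by treatment.

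The cost is one SAP sentence and no new data. The two diary terms use two degrees of freedom. With intercept, treatment, night-1 WASO and stratum, 80 − 6 = 74 remain.
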